##### 2) Items related to safety

- [1] List of occurrence status of adverse reactions and infections
- [2] Factors that may contribute to safety
  - Incidence of adverse reactions by patient characteristics (sex, disease duration, smoking habit, presence or absence of complications, presence or absence of medical history, presence or absence of allergy, presence or absence of previous treatment, and presence or absence of concomitant drugs)
  - According to symptoms of Behcet disease other than gastrointestinal tract symptoms
  - According to changes in steroid dose in patients who receive steroid
- [3] Adverse events that occurred during or after administration of this drug

- List of occurrence status of serious adverse events

[4] Occurrence status of Self-administration error

[5] Contribution to safety when anti-adalimumab antibody is detected

3) Items related to efficacy

[1] Comprehensive evaluation of gastrointestinal symptoms, evaluation of gastrointestinal symptoms Behcet disease, evaluation of main symptoms of Behcet disease, evaluation of accessory symptoms, level of improvement in endoscopy findings, and CRP

[2] Factors considered to contribute to efficacy

- Efficacy by patient characteristics (sex, disease duration, smoking habit, presence or absence of complications, presence or absence of medical history, presence or absence of allergy, presence or absence of previous treatment, and presence or absence of concomitant drugs)
- According to symptoms of gastro-intestinal Behcet disease
- According to changes in steroid dose in patients who receive steroid
- Contribution to efficacy when anti-adalimumab antibody is detected

4) Items concerning patients with specific characteristics

List of occurrence status of adverse reactions/infections in patients with specific characteristics including children, the elderly, expectant and nursing mothers, patients with renal impairment, or patients with hepatic function disorder

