Presence or absence of history of allergy	
If there is a check mark in a box for history of allergy in “patient information” in survey sheet, such patients are deemed to have allergy, and if there is a check mark in a box for “unknown about allergy”, whether patients have allergy is deemed as unknown, and if a column for “presence or absence of allergy” is not completed and in any other situations, patients are deemed to have no history of allergy.

Patients with hepatitis B viral infection	
Patients with description as “hepatitis→ viral” in “complication” and “Type B” in “hepatitis virus carrier” in “patient information”, are deemed to be patients with hepatitis B infection. In addition, patients have events corresponding to MedDRA PT code described in “161207 Hepatitis B (FIX) CRO” are deemed to have hepatitis B infection.

Presence or absence of smoking habit	
If there is a check mark in a box for presence or absence of smoking habit in the survey sheet, patients are deemed to have smoking habit. If there is a check mark in a box for absence of smoking habit in the survey sheet, patients are deemed to have no smoking habit. If there is a check mark in a box for unknown about smoking habit in the survey sheet, whether patients have smoking habit or not is deemed as unknown. If a column for “smoking habit” is not completed, whether patients have smoking habit or not is deemed as not described.

Patients in whom deviation from rules for administration of this drug is noted	
Patients who receive this drug at the dose other than “160 mg→80 mg→40 mg/2 weeks”, “only 160 mg”, or “160 mg→80 mg/2 weeks”, deviation is deemed to have occurred.

Presence or absence of self-administration	
If there is at least one check mark in a column for “Self-administration” in “Administration status” in the survey sheet, the patients are deemed to do self-administration. In any other situations, patients are deemed not to do self-administration.

Presence or absence of self-administration error	
If there is a check mark in a box for “self-administration error was present” in the survey sheet, self-administration error is deemed to be present, and if there is a check mark in a box for “self-administration error was absent”, self-administration is deemed to be absent.
 
In addition, regardless of presence or absence of check mark in

Name of data	Derivation and calculation method

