	
“self-administration error was present” or “self-administration error was absent”, if details are described about onset date of self-administration error, self-administration error is deemed to be present.
 
If there is no description about onset date of self-administration error, whether there is self-administration error or not is deemed as “Unknown/not described”.

Sex	Data should be extracted from an item, sex, in patient information in the survey sheet. If there are multiple check marks or data without description, sex is deemed to be “unknown/not described”.
Pregnancy/lactation	Data should be extracted from pregnancy/lactation in patient information in the survey sheet. If there are multiple check marks or data about pregnancy/lactation is not completed although “female” is chosen as sex, whether the patients correspond to pregnancy/lactation is deemed to be “unknown/not described”. If any description about this item are found, data should not be aggregated as “female” if “female” is not chosen.
Race	Data is extracted from an item, race, in the survey sheet. If there are multiple check marks or data without description, sex is deemed to be “unknown/not described”.
Age	
Data should be extracted from an item, “Year and month of birth”, and the start date of initial administration in the survey sheet.
 
Date of birth should be complemented by the first day of the month and derived by following SAS codes.
 $\text{floor}((\text{intck}('month', birth data, start date of the initial administration) - (\text{day}(\text{start date of the initial administration}) < \text{day}(birth date))))/12)$ 
However, if derivation could not be executed because birth date or start date of the initial administration is incomplete or unknown, age described in the survey sheet should be employed.
 
If derivation could not be executed by birth date and age is not described, age should be defined as “unknown/not described”.

Child	Patients aged younger than 15 should be applicable.
The elderly	Patients aged 65 or older should be applicable.
body weight	Data should be derived from an item, body weight, in patient information in the survey sheet. If there is a check mark in a box for unknown, or data about body weight is not completed, body weight is deemed to be “unknown/not described”.

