Detailed classifications of medical history	tuberculosis, bacterial bronchitis, nontuberculous mycobacterial infection, aplastic anaemia, pancytopenia, malignant tumour, others
Previously used drug/previous treatment	Absent, present, unknown, not described
Classification of biological preparation as previously used drug/previous treatment	Adalimumab, infliximab, others
Classification of drugs other than biological preparation as previously used drug/previous treatment	Biological preparation, aminosalicylic acid preparation, steroid, immunomodulative drug, antibiotic, other previously used drug, operation, other previous treatment
Concomitant drug	Absent, present, unknown, not described
Detailed classification of concomitant drugs	Aminosalicylic acid preparation, oral adrenocortical steroid, immunomodulative drug, immunosuppressive drug, enteral nutrient, colchicine, others
Combination therapy	Absent, present, unknown, not described
Detailed classification of combination therapy	Operation, others
Endoscopy	Absent, present, unknown, not described

data	Method of dividing hierarchy
Detailed classifications of endoscopy	Ileocecum, colon, esophagus, others
Level of improvement in endoscopy findings	Remission or scar, shrinkage, no change, aggravation, not assessed
Evaluation of gastrointestinal symptoms	
0,1,2,3,4
 
0: No symptom
 
1: There was symptom in last 2 weeks but daily living activities were rarely disturbed.
 
2: There was symptom in last 2 weeks and daily living activities were slightly disturbed.
 
3: There was symptom in last 2 weeks and daily living activities were disturbed.
 
4: There was symptom in last 2 weeks and daily living activities were severely disturbed.

Detailed classifications of gastrointestinal symptoms	Abdominal pain, diarrhoea, others (including bloating, abdominal tenderness, haemorrhage)
Self-administration	Absent, present
Self-administration error	Absent, present, unknown, not described
Drug used after the discontinuation of this drug	Absent, present, unknown, not described
Detailed classifications of drug used after the discontinuation of this drug	Aminosalicylic acid preparation, steroid, immunomodulative drug, biological preparation, other drug
Level of overall improvement	Significant improvement, improvement, ineffective
Detailed classifications of level of overall improvement for patients with improvement or higher level of improvement	Significant improvement, improvement

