#### “1.13 Distribution of self-administration”

Patients included in analysis: Patients included in safety analysis

Objective of analysis: Distribution of presence or absence of self-administration and self-administration error is shown.

Analysis items: The number of patients included in analysis should be calculated.

The number of patients by “self-administration” defined in “11 method of dividing hierarchy of data” and rate of these patients to those included in analysis should be

calculated. In addition, the number of patients with “self-administration error” and rate of these patients to patients in whom self-administration is present should be calculated.

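### The self-administration error derivation contradicts itself for every survey sheet with a ticked box and no onset date, and states no order of precedence

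*SAP*

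**What the plan says.** SAP Section 10.1, in the entry on presence or absence of self-administration error, gives the following rules in this order.

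- **Boxes.** A tick for error present decides the class: "in the survey sheet, self-administration error is deemed to be present". A tick for error absent leads to "self-administration is deemed to be absent". The second wording names self-administration where the error is evidently meant, because self-administration has its own derivation directly above.
- **Onset date given.** Whatever is ticked, "if details are described about onset date of self-administration error, self-administration error is deemed to be present".
- **No onset date given.** "If there is no description about onset date of self-administration error, whether there is self-administration error or not is deemed as" unknown/not described. The sentence places no condition on the boxes.

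Section 11 lists the classes of this variable as "Absent, present, unknown, not described". Section 5.1 names "Occurrence status of Self-administration error" as the fourth of five safety items. Table 1.13 asks for the number of patients with an error and the "rate of these patients to patients in whom self-administration is present". The patient list (Table 1.4) carries a flag for patients with a self-administration error.

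**The concern.** The date override is given explicit precedence over the boxes. The no-date sentence is given none, yet it covers every sheet without a date, including sheets on which a box has already settled the answer. A patient with no error has no error date to report, so the sheets correctly ticked absent are the ones it catches. It also catches a sheet on which the physician ticked present but gave no date.

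Table 1.13 is the only tabulation of a listed safety item. Two programmers working from this text could produce different counts from the same data, and one of those versions would understate reported errors.

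**Working it through.** The SAP has no figure to reproduce here. The check runs the written rules over every combination of box (present, absent, both, neither) and onset date (described, not described): 4 × 2 = 8 combinations. Three readings are compared:

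- all rules applied at once;
- rules applied in written order, so the last applicable sentence wins;
- the no-date sentence limited to sheets with neither box ticked.

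| Box ticked | Onset date | All rules at once | Written order | No-date sentence limited to blank sheets |
|---|---|---|---|---|
| present | yes | present | present | present |
| present | no | present + unknown | unknown | present |
| absent | yes | absent + present (settled by the date override) | present | present |
| absent | no | absent + unknown | unknown | absent |
| both | yes | absent + present (settled by the date override) | present | present |
| both | no | absent + present + unknown | unknown | not settled |
| neither | yes | present | present | present |
| neither | no | unknown | unknown | unknown |

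What follows from the table:

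1. With all rules applied at once, three of the four undated rows (every undated row with a tick) carry conflicting classes, and no stated precedence resolves them.
2. In written order the boxes have no effect. A date gives present and no date gives unknown. Absent is reached in 0 of 8 combinations, although Section 11 lists it.
3. With the last sentence limited to blank sheets, present, absent and unknown/not described can all be reached. Only the sheet with both boxes ticked and no date still lacks a rule.

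Effect on the Table 1.13 rate in written order. Let N be the self-administering patients, E those ticked present, and u the share of E without a date. Assume that no sheet ticked absent or left blank has a date.

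- Rate with undated ticks counted: E / N.
- Rate in written order: E × (1 − u) / N.
- Ratio of the second to the first: 1 − u. The relative understatement equals u.

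Illustration with assumed figures, none of them in the SAP: N = 100, of whom 10 are ticked present, 80 ticked absent and 10 blank.

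| Ticked errors without a date | Rate shown | Absent | Unknown |
|---|---|---|---|
| 0 | 10/100 = 10% | 0 | 80 + 10 + 0 = 90 |
| 2 | 8/100 = 8% | 0 | 80 + 10 + 2 = 92 |
| 5 | 5/100 = 5% | 0 | 80 + 10 + 5 = 95 |
| 10 | 0/100 = 0% | 0 | 80 + 10 + 10 = 100 |

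Under the limited reading, the same sheets give 10 present, 80 absent and 10 unknown, a rate of 10%, in every row.

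The first row shows that moving the 80 absent patients to unknown leaves the rate at 10%. The numerator counts only errors, the denominator is all self-administering patients, and Section 9.2 keeps unknown and not-described patients in denominators. Only ticked but undated errors can change the rate.

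**The case against.** The case for leaving the text alone is that the last sentence is a residual rule with a clause missing. Section 11 lists absent, so that class is meant to be used. Neighbouring entries in Section 10.1 treat unknown/not described as what is left over: the tuberculin/IGRA and hepatitis B test entries use it for everything not already classed, and smoking habit is not described only when its column is not completed. On that reading no error is lost and absent is populated. Further, the last sentence asks only for some description of an onset date, so a partial date may count, which would shrink the affected group.

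Much of this stands. A reader might infer from the last sentence that the plan discards undated errors and leaves absent permanently empty. The document does not support that as a settled outcome, because the same entry classes ticked sheets by their box and nothing says the last sentence overrides it. A reader might also infer that sending absent patients to unknown distorts the error rate, which it does not.

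What does not stand is the idea that the text already expresses the residual rule. The neighbouring entries write the residual condition out. This one uses a different trigger, the absence of an onset date, and the programmer would have to supply the condition on the boxes.

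**Conclusion.** The derivation is internally contradictory for ticked, undated sheets and needs correcting. The probable intention is that unknown/not described applies when neither box is ticked and no date is given, but the SAP does not say so.

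If the last sentence is applied as written, there are two effects. The Table 1.13 error rate is understated by the share of ticked errors without a date. The absent class cannot be reached, so the derivation no longer separates patients without an error from patients with nothing reported.

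The absolute size of the first effect cannot be stated, because the SAP gives neither the error rate nor the undated share. The figures in the illustration are assumptions.

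The reach is small: one descriptive table and one listing flag. The factor analyses in Tables 2.9 and 3.4 and the stratified Table 2.5 use self-administration itself, not the error, so no test, adverse reaction incidence or responder rate depends on this variable.

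**What to change.** Replace the entry in Section 10.1 with an ordered rule:

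1. Present, if the present box is ticked or any onset date of an error is described.
2. Otherwise absent, if the absent box is ticked.
3. Otherwise unknown/not described.

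Step 1 keeps the existing date override and also settles the sheet with both boxes ticked and no date, which becomes present. In the same edit, correct the wording for the absent box so that it names the error.

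In Table 1.13, ask explicitly for all three classes, each over the self-administering patients already used as the denominator.

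The cost is a short wording change in the SAP, about one line of code and two further rows in one table. No new data are needed.

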Body height	Data should be derived from an item, body height, in patient information in the survey sheet. If there is a check mark in a box for unknown, or data about body height is not completed, body height is deemed to be “unknown/not described”.
BMI	$\text{Body weight (kg)} / (\text{body height(cm)})^2$
Disease duration (Year)	“YY/MM” in “disease duration” in “patient information” should be converted to description on an annual basis.

Name of data	Derivation and calculation method
	
In a case where there are both values for year and month: Year + month/12
 
In a case where there is only value for year: Year
 
In a case where there is only value for month: Month/12
 
In any other situations, disease duration should be defined to be “unknown/not described” as derivation cannot be executed.

Reasons for use	If there are duplicated check marks in gastro-intestinal Behcet disease and other conditions for reasons for use, data should be aggregated as “gastro-intestinal Behcet disease”.
• Diagnostic classifications of gastro-intestinal Behcet disease	
Diagnostic classification should be determined based on check marks in boxes for main symptoms and accessory symptoms in the survey sheet.
 
 
• Complete type: 4 items of main symptoms
 
• Incomplete type: Any of following conditions are met 
 
[1] Any 3 items of main symptoms
 
[2] Any 2 items of main symptoms and 2 items of accessory items
 
[3] Either item of eye symptoms of main symptoms or any main symptoms other than eye symptoms
 
[4] Either item of eye symptoms of main symptoms or any 2 accessory symptoms
 
 
 
• Suspected: In a case where at least 1 main symptom is met although conditions for incomplete type are not met
 
• Other: There is no main symptom
 
• Unknown/not described: Other than above situations
 

Tuberculin test or IGRA test	
Tests were implemented: Either of “Tuberculin test” or “Interferon <math>\gamma</math> free release test” is implemented (if there is no check mark in box for implementation although test results are described, tests are deemed to have been implemented”.
 
Test were not implemented: Both “Tuberculin test” and “Interferon <math>\gamma</math> free release test” were not implemented.
 
Unknown/not described: Other than above situations

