## 11. Method of dividing hierarchy of data

data	Method of dividing hierarchy
Dosage and administration	160mg→80mg→40mg/2 weeks, no changes thereafter 160mg→80mg→40mg/2 weeks, and 160mg or 80mg is administered at least once thereafter 160mg, and not administered thereafter 160mg→80mg, and not administered thereafter 80mg, and not administered thereafter 40mg, and not administered thereafter others
the number of administrations	at least once and less than 4 times at least 4 times and less than 12 times at least 12 times and less than 26 times at least 26 times and less than 39 times at least 39 times and less than 52 times at least 52 times and less than 65 times at least 65 times and less than 78 times at least 78 times
Total dose	lower than 500mg at least 500mg and lower than 1000mg at least 1000mg and lower than 2000mg, at least 2000mg and lower than 3000mg at least 3000mg unknown
Mean daily dose	lower than 40 mg at least 40 mg and lower than 60 mg at least 60 mg and lower than 80 mg at least 80 mg and lower than 100 mg at least 100 mg unknown

data	Method of dividing hierarchy
Administration duration	at least 0 week and shorter than 4 weeks (1-28 days) at least 4 week and shorter than 12 weeks (29-84 days) at least 12 weeks and shorter than 24 weeks (85-168 days) at least 24 weeks and shorter than 52 weeks (169-364 days) at least 52 weeks and shorter than 104 weeks (365-728 days) at least 104 week and shorter than 156 weeks (729-1093 days) unknown * When the start date of the administration is defined as 1
Reasons for discontinuation	Occurrence of adverse events, insufficient effect, patient's request, not visiting, others, multiple reasons, unknown, and not described
Sex	male, female, unknown, not described
Pregnancy/lactation	Without pregnancy/lactation, during pregnancy, during lactation, unknown, not described
Race	Japanese, other Asians, others, unknown, not described
Age (years)	Younger than 15 years, 15 years or older and younger than 65 years, 65 years or older, unknown/not described
Body weight (kg)	Lower than 30, 30 or higher and lower than 40, 40 or higher and lower than 50m, 50 or higher and lower than 60, 60 or higher, unknown/not described
Body height (cm)	Lower than 140, 140 or higher and lower than 150, 150 or higher and lower than 160, 160 or higher and lower than 170, 170 or higher and lower than 180, 180 or higher and lower than 190, 190 or higher, unknown/not described

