BMI	Younger than 18.5 years, 18.5 years or older and younger than 25 years, 25 years or older and younger than 30 years, 30 years or older, unknown
Smoking habit	Absent, present, unknown, not described
Disease duration (years)	Shorter than 2, 2 or longer and shorter than 5, 5 or longer and shorter than 10, 10 or longer, unknown/not described
Reasons for use	Gastro-intestinal Behcet disease, other conditions, unknown, not described
Diagnostic classifications of Behcet disease	Complete type, incomplete type, suspected, others, unknown/not described
Main symptoms of Behcet disease	Recurrent oral mucosa aphthous ulcer, cutaneous symptoms, eye symptoms, ulcer of vulva
Evaluation of main symptoms of Bechet disease	0,1,2,3 Recurrent oral mucosa aphthous ulcer Cutaneous symptoms (erythema nodosum, subcutaneous phlebitis, folliculitis-like skin eruption, acne-like skin eruption) Ulcer of vulva Eye symptoms
Presence or absence of eye symptoms of	There is no symptom: Point for evaluation of main symptoms of Bechet disease is 0

data	Method of dividing hierarchy
Bechet disease	There are any symptoms: Points for evaluation of main symptoms of Bechet disease are 1,2,3 Unknown/not described: Other than above situations
Accessory symptoms of Bechet disease	Arthritis without deformity or rigidity, epididymitis, gastrointestinal lesions characterized by ulcer of ileocecum, vascular lesion, moderate or higher degree central nervous lesion
Presence or absence of accessory symptoms of Bechet disease	There are any symptoms: there are check marks in boxes for each accessory symptom There is no symptom: Other than above
History of allergy	Absent, present, unknown, not described
Tuberculin test or IGRA test	Not implemented, implemented, unknown, not described
HBs antigen	Not implemented, implemented, unknown, not described
HBs antibody	Not implemented, implemented, unknown, not described
HBc antibody	Not implemented, implemented, unknown, not described
HBV-DNA quantitative	Not implemented, implemented, unknown, not described
Complications	Absent, present, unknown, not described
Detailed classification of complications	Liver disorder, renal disorder, circulatory disorder, blood disorder, respiratory disorder, others
Other classifications of complications	Diabetes mellitus, gastrointestinal disorder, osteoporosis, malignant tumour, collagen disorder, others
Medical history	Absent, present, unknown, not described

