## “1.12.1 Distribution of patient characteristics”

Patients included in analysis: Patients included in safety analysis, patients included in efficacy analysis, patients whose survey sheet data was fixed

Objective of analysis: Distribution of patient characteristics is shown

Analysis items: The number of patients included in analysis should be calculated.

The number of patients according to following classifications defined in “11 method of dividing hierarchy of data” and rate of these patients to those included in analysis should be calculated.

Sex, pregnancy/lactation, race, age (years), body weight (kg), body height (cm), BMI (kg/m^2), smoking habit, disease duration (years), reasons for use, diagnostic classifications of Behcet disease, main symptoms of Behcet disease, accessory symptoms of Behcet disease, allergy history, tests for tuberculosis, test for hepatitis B, complications, detailed classifications of complications (liver disorder, renal disorder), medical history, previously used drug/previous treatment, classifications of biological preparations as previously used drug/previous treatment, classifications of drugs other than biological preparations as previously used drug/previous treatment, concomitant drugs, detailed classifications of concomitant drugs, combination therapy, detailed classifications of combination therapy, endoscopy, detailed classifications of endoscopy

In addition, summary statistics should be calculated for following items.

Age (years), body weight (kg), body height (cm), BMI (kg/m^2), disease duration (years)

Notes: Rate of pregnancy/lactation should be calculated as that to female patients.

In addition, breakdown of each item should be represent the rate of patients to the aggregated number of patients corresponding to the item at one-step higher hierarchical level.

(Example: Rate of patients according to detailed classifications of complication to all patients who have complications should be calculated)

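### The BMI formula uses height in centimetres, so every calculable value falls below 18.5, and the BMI bands are labelled as ages in years

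*SAP*

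**What the plan says.** Three places in the SAP bear on BMI.

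- **Section 10.1 (derivation).** The numerator is "Body weight (kg" and the denominator is the square of "body height(cm". There is no division by 100 and no factor of 10,000. The row for body height takes the value from the survey sheet and mentions no conversion to metres.
- **Section 11 (bands).** The BMI classes read "Younger than 18.5 years, 18.5 years or older and younger than 25 years, 25 years or older and younger than 30 years", followed by a top class from 30 and an unknown class.
- **Section 13.1, Table 1.12.1 (output).** The table lists "BMI (kg/m 2 ), smoking habit" among the characteristics to be tabulated by band. It names BMI again, in the same unit, among the items for summary statistics. It is produced for the safety population, the efficacy population and all patients with fixed survey sheets.

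BMI is also a column in the listing of patients aged 18 or younger (listing 14.3). The revision history, through version 1.2, records no correction to the formula or the bands.

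**The concern.** The derivation gives a quantity in kg/cm2, while the output table asks for kg/m2. Section 10 is where the SAP fixes how variables are computed, so a program that follows it exactly would be faithful to the SAP and still give wrong numbers. The bands in section 11 should settle which scale is meant, but they are worded as ages.

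At stake is the BMI part of the description of who was treated. Section 3.1 says that some or all of the results go into reporting to the regulator and into the reassessment application. A table showing every patient with a calculable BMI as below 18.5 would misdescribe the population there.

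**Working it through.** **Inputs from the SAP**

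- Formula: weight (kg) / height (cm)^2 (section 10.1).
- Reporting unit: kg/m2 (Table 1.12.1).
- Cut-offs: 18.5, 25 and 30 (section 11).
- Height scale: section 11 bands height in centimetres, beginning "Lower than 140, 140 or higher and lower than 150, 150 or higher and lower than 160" and ending at 190 or higher.
- Weight scale: section 11 bands weight in kilograms, beginning "Lower than 30, 30 or higher and lower than 40" and ending at 60 or higher.

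The SAP gives no worked BMI value to reproduce. The individual weights and heights below are assumed for illustration.

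**Scale factor**

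Height in metres is h/100, with h in centimetres. BMI in kg/m2 is w / (h/100)^2 = 10,000 × w / h^2. The formula as written gives w / h^2, which is too small by a factor of 10,000 whatever the patient's size.

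**Single example, 60 kg and 165 cm**

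- As written: 60 / 165^2 = 60 / 27,225 = 0.0022.
- With metres: 60 / 1.65^2 = 60 / 2.7225 = 22.04.

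**60 kg across the height range**

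| Height (cm) | As written | kg/m2 | Band on the kg/m2 scale |
|---|---|---|---|
| 140 | 0.003061 | 30.61 | 30 or higher |
| 150 | 0.002667 | 26.67 | 25 to below 30 |
| 160 | 0.002344 | 23.44 | 18.5 to below 25 |
| 170 | 0.002076 | 20.76 | 18.5 to below 25 |
| 190 | 0.001662 | 16.62 | below 18.5 |

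On the kg/m2 scale these patients spread over all four bands. As written, all five are in the lowest.

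**Could any patient leave the lowest band?**

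Over 30 to 150 kg and 100 to 190 cm, the formula as written runs from 30 / 190^2 = 0.0008 to 150 / 100^2 = 0.015. Even 300 kg at 100 cm gives 0.03. Reaching 18.5 needs a weight of 18.5 × h^2:

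- 100 cm: 185,000 kg
- 140 cm: 362,600 kg
- 165 cm: 18.5 × 27,225, or about 503,660 kg

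So no patient can leave the lowest band.

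**Where BMI is used**

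BMI appears in Table 1.12.1 (bands and summary statistics) and in listing 14.3. It is not among the patient characteristics tested in Table 2.9 (adverse reactions) or Table 3.4 (overall improvement). It does not enter the population definitions in section 8, the incidence definition in section 10.2 or the efficacy definitions in section 10.3.

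**The case against.** The best defence is that the intention is obvious. Table 1.12.1 names the unit, the cut-offs are recognisable on that scale, and the centimetre label in the formula can be read as naming only the unit of the input. A value of 0.002 with all calculable patients in one band would be noticed at the first table run. The age wording has no numerical effect, since the numbers and the direction of each cut remain usable, and it may be a translation slip. Body weight and height are also tabulated directly in Table 1.12.1, and no test depends on BMI.

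Much of this stands as a limit on the consequence. The error is conspicuous, its reach is descriptive, and the years wording is a labelling fault. It is also right that patients without height or weight would be unknown, so the effect applies to patients with both recorded.

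It does not rescue the text. A correct table would require the programmer to depart from the written derivation, and a check of the program against that derivation would pass the wrong values. Translation might explain the word years, but it would not explain a formula without the conversion.

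**Conclusion.** The concern holds. As written, the BMI derivation contradicts the unit in Table 1.12.1 by a factor of 10,000. It places 100% of patients with recorded height and weight below 18.5. The BMI bands carry the wrong label and unit. The BMI rows of Table 1.12.1, in all three populations, and the BMI column of listing 14.3 would be wrong. No hypothesis test, safety incidence or efficacy rate is affected.

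The conclusion assumes only that height enters the formula in centimetres, as the formula states and the section 11 height bands confirm. It does not depend on the illustrative weights and heights, because the factor of 10,000 is the same for every patient. The text should be corrected, though the consequence is confined to description.

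**What to change.** Two wording changes in the SAP:

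1. **Section 10.1:** BMI (kg/m2) = body weight (kg) / (body height (cm) / 100)^2.
2. **Section 11:** BMI bands of below 18.5, 18.5 to below 25, 25 to below 30, and 30 or higher, all in kg/m2, keeping the unknown class.

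No new data are needed and no other analysis is altered. If BMI has already been programmed, check which formula the code uses, and rerun Table 1.12.1 and listing 14.3 if it follows the written one.
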